#### Relationship of endogenous DA release to anxiety and/or inhibition in AN and BN:

**Background:** Considerable literature (see ) shows that HA, a multifaceted temperament trait that contains elements of anxiety, inhibition, and inflexibility, is elevated in individuals who are ill with AN and BN and persists after recovery. As noted above, DC [C]raclopride BPND is positively correlated with HA. Importantly, increased DA D2-like receptor functional activity is associated with inhibition in healthy humans. Moreover, rats characterized as risk averse show greater D2 mRNA expression in the DC. In Aim 2C, we seek to explore how DA signaling in associative /executive cortical striatal circuitry may be related to inhibition and/or adverse consequences in AN and BN.

**Anxiety:** The major goal in Aim 2c is to replicate and extend our finding that self-reports of HA are associated with baseline D2 binding in the DC in AN and BN, and self-reports of anxiety are

**Figure 1:** Predicted relationship between SSRT and baseline [C]racloprideBPND. Gray shade, range of individual responses; ●, mean CW values; O, mean AN values at baseline; →, predicted change when post-AMPH SSRT is compared with baseline [C]racloprideBPND.

associated with endogenous DA release in the DC in AN. Our pilot data in REC AN show AMPH stimulated anxiety and this was positively associated with the magnitude of DA release in the DC. This is different from studies in controls, who tend to become euphoric after AMPH in association with AVS stimulant-induced striatal DA release. Most people find eating to be a pleasant and rewarding experience. But for AN, eating stimulates dysphoric mood, while there is an anxiety-reducing character to dietary restraint and reduced caloric intake. Ingestion of palatable food is associated with striatal endogenous DA release. We hypothesize that food-induced release of DA activates DC D2 receptors resulting in anxiety in AN (and not AVS related reward and motivation as in healthy controls). As a result, AN individuals pursue starvation because food refusal may be a way of diminishing DA release and concomitant anxiety. In fact, AN individuals have decreased CSF HVA, the major metabolite of DA, supporting this hypothesis. Predicting response in REC BN and AN-BN is more speculative. We may find a heterogeneous response to AMPH in REC BN and AN-BN. In those who have high HA traits, we expect to find that AMPH administration makes them more anxious, and that anxiety will be associated with increased endogenous DA in associative and sensorimotor striatal regions. There may also be a group that becomes euphoric on AMPH. Broft reported evidence of an association between striatal DA response and ratings of “energetic” in ill BN but these were said to be driven by a small number of data points. This group, which may be at higher risk for substance abuse, may have diminished endogenous DA in associative regions, or enhanced AVS DA release associated with pleasure.

**Inhibition:** Clinically, it is well known that AN have exaggerated self-control and are anhedonic so they are able to sustain self-denial of food as well as most comforts and pleasures in life. For example, AN have an enhanced ability to delay reward (i.e., show less reduction in the value of a monetary reward over time) compared to healthy volunteers. This enhanced cognitive control and ability to delay reward may help to maintain persistent food restriction. We will build on a recent study in healthy controls that showed that striatal (particularly in dorsal regions) DA D2/D3 receptor availability was negatively correlated with speed of response inhibition [stop signal reaction time (SSRT)] and positively correlated with inhibition-related fMRI activation in frontostriatal neural circuitry. Thus people with faster stopping speed had more D2 receptor binding in the caudate and putamen. The stop signal task (SST) requires people to stop an already initiated response and calculates the speed of stopping (SSRT). There are relatively little response inhibition data (with SST or any other task) in AN, but a recent study in AN found that they had longer SSRT. Our data show that AN have normal DC D2 binding. However, as noted above, there is evidence that ill and recovered AN have reduced endogenous DA. Because AN may have less DA activating the DA D2 receptors, this may explain why their average inhibition ability is impaired. We will administer the SST after subjects complete the baseline [C]raclopride PET study. We predict (**Figure 1**) that both AN and CW will show a negative relationship between SSRT and DC D2 binding, but that such a relationship in AN will be shifted to the left due to reduced DA activation of the D2 receptor. While slower inhibition in AN may seem counter-intuitive, this finding may be consistent with studies that show they have impaired abilities to change mental set.

We will repeat the SST after administration of AMPH. Studies tend to show that AMPH improves inhibition in healthy people without changing “going” speed. That is consistent with the idea that AMPH induced release of endogenous DA increases activation of D2 receptors and thus underlies inhibition-related caudate activity. We expect to find that AMPH shifts healthy controls to the right (**Figure 1**). An abnormal shift to the right in AN would suggest aberrant function of DA/D2-related processes. It is possible that higher anxiety in AN contributes to the slower stopping speed. While low threat puts people in a state of arousal where they can stop things more quickly, high threat association appears to make them slower. We will stratify our AN population into high and low state anxiety groups to better understand the relationship between anxiety and response inhibition ability in this group, and how that relates to the AMPH challenge and a putative marker of endogenous DA. Overall, too few data exist to be certain that the SST is an adequate reflection of inhibitory control ability in AN (especially in a way that relates to self-control). Individuals with BN and AN-BN have a puzzling group of symptoms in that they alternate between being overly inhibited and overly disinhibited: eating behaviors tend to alternate between restriction and overeating with a loss of normal meal patterns. This study will provide the opportunity to better understand relationships between [C]raclopride

BPND or DA release and measures of inhibition and anxiety in BN and AN-BN.

**Significance:** The understanding of the pathophysiology of EDs has tended to lag behind other major psychiatric disorders. Improvement in the understanding and treatment of EDs are of immense clinical and public health importance as these are often chronic, relapsing illnesses with substantial and costly medical morbidity, and a high mortality. AN and BN have puzzling symptoms that are unique to the disorders: extremes of eating (restricting, bingeing/purging), relentless drive to lose weight, body image distortions, denial of illness, etc. We have little understanding of how such symptoms are encoded in the brain. These symptoms appear to be unique to humans. Since animal models have not been developed displaying these puzzling symptoms, studies in humans are essential. The overarching goal of this, and related applications, is to use imaging to understand the neural circuitry of AN and BN and how symptoms are encoded in these circuits.

Importantly, for AN, there is no proven treatment that reverses symptoms or FDA approved medication. While those with BN may respond better to treatment, many continue to be symptomatic or relapse. Despite the evidence of 5-HT and DA disturbances in ED, there is little evidence that selective 5-HT reuptake inhibitors (SSRIs) or the neuroleptics pimozide and sulpiride stimulate weight gain or reduce core symptoms in ill AN. Moreover, it remains controversial as to whether SSRIs reduce relapse after weight gain. Still, preliminary data suggest that atypicals, such as olanzapine, quetiapine, risperidone, and aripiprazole may be useful in reducing anxiety and promoting weight gain in ill AN. Many of the psychoactive medications that are approved for use in humans act on 5-HT and DA pathways. Thus, a better understanding of how 5-HT and DA contribute to symptoms in ED may help us advance beyond the trial and error system and develop new methods for identifying effective medications and psychological treatments.

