In **AIM 2B**, we will assess endogenous striatal DA release in order to better understand altered striatal [C]raclopride binding, and (in **AIM 2C**) to replicate and extend pilot data that show that endogenous DA release in the dorsal caudate (DC) provokes inhibitory and anxiety symptoms in AN and BN. In brief, because [C]raclopride binding is influenced by endogenous DA, elevated [C]raclopride binding could indicate either an elevation of the density and/or affinity of the DA D2/D3 receptors or a reduction of intrasynaptic DA concentrations. It has been shown in non-human primate studies that the decrease in the BPND of benzamide radiotracers such as [C]raclopride following amphetamine (AMPH)-induced DA release is a reliable measure of endogenous DA transmission in striatal subdivisions (limbic, associative and sensorimotor striatum). AMPH administration results in an increase in extracellular DA and a consequent reduction in [C]raclopride binding. The change ( $\Delta$ ) in BPND (the difference between the [C]raclopride BPND at baseline and post-AMPH treatment normalized to the baseline BPND and expressed as a percentage) provides a non-invasive measure of changes in DA concentration in the human brain. We will use the PET/double [C]raclopride/AMPH paradigm described above to assess striatal endogenous DA release. Several recent, small scale studies using this technology and a previous study of cerebral spinal fluid (CSF) homovanillic acid (HVA), a DA metabolite, support the likelihood that REC AN and BN have alterations of endogenous striatal DA release. In AIM 2B we will assess endogenous DA release to help interpret alterations in DA functional activity as well as D2/D3 receptors in limbic, associative, and sensorimotor striatal regions. As summarized in **Table 1** we predict that endogenous DA release will be selectively diminished in limbic striatal regions in REC AN and in associative and sensorimotor regions in REC BN. These data argue that AN have diminished ability to direct “motivated” responses whereas BN may have hypoactive dorsal associative inhibitory pathways. Several lines of evidence support our hypothesis that alterations of food-induced DA secretion, perhaps acting on DA D2 receptors, contribute to pathologic eating. In **AIM 2C** we seek to replicate and extend findings that AN have a paradoxical response to palatable foods because endogenous DA release in the DC is anxiogenic in AN. This anxiogenic effect is compensated for by restricted eating to avoid anxiety. We will also test the hypothesis that a measure of altered inhibition in AN is associated with DC DA D2 binding.

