**Aim 2C** Relationships between [C]raclopride  $\Delta$  BPND and behavioral characteristics (from assessments and VAS scales) and plasma AMPH levels of subjects will be analyzed with Pearson Product-Moment correlation coefficient. For example, we will compare the Fisher's z-transformed correlations between behavioral measures of euphoria and anxiety with [C]raclopride  $\Delta$  BPND in REC AN, REC AN-BN and REC BN vs. CW using a t-test. Based on our pilot data in REC AN, we expect correlations between euphoria and [C]raclopride  $\Delta$  BPND in the AVS to be larger (in magnitude) than -0.69 in CW and 0.21 in REC AN subjects. Assuming a difference in Fisher's z-transformed correlations of 1.06 (or larger), we will have power 0.91 to see a group difference at the 0.05 level (two-sided), with 20 subjects per group. (Note that the z-transformed value of 0.69 is -0.85, and the z-transformed value of 0.21 is 0.21, giving a difference of 0.21 - (-0.85) = 1.06). Similarly, we will correlate DA release with self-ratings of anxiety, euphoria, self-control, and labile mood in striatal regions in order to assess behavioral response, as well as SSRT and post-study food consumption. We will use continuous

measures of impulse control and inhibition including the SSS, BIS-11, EDI-2-subscale impulse regulation, novelty seeking and HA from the TCI and the basic stop signal task. It is not certain what to expect from the REC BN and REC AN-BN subjects, but we will look for differences in correlations in the same way. Assuming these differences are larger than 0.909, we will have power in excess of 0.80 to see group differences at the 0.05 level (two-sided). We will explore the effects of age, height, and weight on DA release using partial correlations, after controlling for these variables.

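### Aim 2C ties anxiety in recovered AN to dopamine release in the dorsal caudate, but no planned test separates the dorsal caudate from the AVS or from overall striatal release

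*Combined protocol and SAP*

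**What the plan says.** Section 6 (Specific Aims) says Aim 2C seeks to replicate and extend findings that "endogenous DA release in the DC is anxiogenic in AN". The section 7 text on endogenous DA release, anxiety and inhibition makes this the major goal of the aim. It cites pilot data in REC AN in which "AMPH stimulated anxiety and this was positively associated with the magnitude of DA release in the DC", contrasts this with controls, in whom AVS release goes with euphoria, and builds an account of food refusal on the hypothesis that food-induced "release of DA activates DC D2 receptors resulting in anxiety in AN (and not AVS related reward and motivation as in healthy controls".

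The analysis is in section 9, Power and Statistical Analysis Plan, Aim 2C:
- Relationships between release and behaviour "will be analyzed with Pearson Product-Moment correlation coefficient".
- Fisher z-transformed correlations are compared "in REC AN, REC AN-BN and REC BN vs. CW using a t-test", that is, between groups.
- "we will correlate DA release with self-ratings of anxiety, euphoria, self-control, and labile mood in striatal regions".
- "We will explore the effects of age, height, and weight on DA release using partial correlations, after controlling for these variables".

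The one worked power example concerns euphoria and AVS release, with correlations expected "in the AVS to be larger (in magnitude) than -0.69 in CW and 0.21 in REC AN subjects". There is none for anxiety and DC release. The Neuroimage Analysis section makes the AVS the limbic subdivision and places the DC in the associative subdivision, so both regions are measured in every woman.

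**The concern.** The hypothesis names a site; the planned tests ask only whether release at that site is associated with the rating. Each woman receives one oral dose and has one post-amphetamine scan, so women with a large response in one striatal region may well have a large response in another. If so, anxiety that depends on AVS release, or on release across the striatum, will also correlate with DC release.

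Nothing in the plan sets the two regions against each other for the same rating. The z comparison is between groups, release in another region is never a covariate, and the limbic/associative balance in Table 1 is a model with no test attached. Aim 2B compares mean release between groups, which is a different question. The argument that AN women restrict food to avoid DC-mediated anxiety depends on the site, and a significant DC correlation could be taken as support that the test does not give.

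**Working it through.** **The plan's own figure.** atanh(0.69) + atanh(0.21) = 0.848 + 0.213 = 1.061, as stated. With 20 per group and variance 1/n for each z: 1.06/√(2/20) = 3.352; 3.352 − 1.960 = 1.392; power 0.918 (0.904 from a t-test on 38 df), which brackets the stated 0.91. With the usual variance 1/(n − 3): 1.06/√(2/17) = 3.090; 3.090 − 1.960 = 1.130; power 0.871. Either way, the figure describes a between-group contrast for euphoria and AVS, not a contrast between regions.

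**Inputs for the regional question.**
- n = 20 (the Aim 2C power statement) and n = 25 (planned completers, section 10); two-sided 0.05.
- ρ, the DC–AVS correlation of release: not in the documents; assumed 0.5–0.85.
- r, the true correlation of anxiety with release in the driving region: not in the documents; assumed 0.5–0.69. The upper value is the size the plan uses for euphoria and AVS in CW. The plan's REC AN value for euphoria and AVS, 0.21, is run separately.
- Release is coded so that a larger value means more release; the plan's −0.69 reflects the sign of ΔBPND.

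**Formulas.** If anxiety depends on AVS only, the induced DC correlation is r × ρ, from 0.5 × 0.5 = 0.25 to 0.69 × 0.85 = 0.587. At n = 25 a Pearson correlation is significant above 2.069/√(23 + 2.069²) = 0.396. A hand check with Fisher's z gives (atanh 0.25 − atanh 0.396) × √22 = −0.77, or about 22%, and (atanh 0.587 − atanh 0.396) × √22 = 1.19, or about 88%, close to the simulated ends below.

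The joint-model test is the partial correlation of anxiety with DC given AVS, on n − 3 df. Williams' statistic, also on n − 3 df, is t = (r_DC − r_AVS) × √{(n − 1)(1 + ρ) / [2R(n − 1)/(n − 3) + m²(1 − ρ)³]}, where R is the determinant of the 3 × 3 correlation matrix, m is the mean of r_DC and r_AVS, and sample values are used.

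**Simulation** (trivariate normal, 40,000 runs per cell, r = 0.5–0.69, ρ = 0.5–0.85; entries count significance in the DC-positive direction, nominal 2.5%):

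| What drives anxiety | n | DC Pearson | DC term given AVS | Williams, DC > AVS |
|---|---|---|---|---|
| AVS only | 20 | 18–81% | about 2.5% | under 1% |
| AVS only | 25 | 23–90% | about 2.5% | under 1% |
| Both equally | 20 | 64–95% | 10–72% | about 2.5% |
| Both equally | 25 | 75–98% | 12–83% | about 2.5% |
| DC only | 20 | 64–95% | 23–87% | 9–46% |
| DC only | 25 | 75–98% | 28–94% | 11–57% |

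The DC Pearson ranges are the same whether DC alone or both regions equally are linked to anxiety, so that test carries no information on which of these holds. With r = 0.21 and AVS as the only driver, DC is significant in about 7–14% of trials across n = 20–25.

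In the AVS-only case with r = 0.5–0.69, when DC is significant AVS is also significant in 86–99.7% of trials. DC significant with AVS not significant occurs in 0.2–3.5%.

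**The case against.** The plan correlates ratings with release in striatal regions, and the AVS is one of them, so the AVS–anxiety result would be at hand. A reader might infer that an AVS link would be reported as a DC link and that 23–90% is the rate of wrong conclusions. The documents do not support that: a careful analyst shown both correlations would usually see both significant. What remains is that nothing requires the comparison or says how to read two significant regions.

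A reader might also infer that the plan claims anxiety in AN has nothing to do with the AVS. It does not. The parenthesis in the quoted sentence contrasts reward in controls with anxiety in AN, the sentence concerns food-induced release and is a hypothesis, and the test uses amphetamine. The Aim 2C goal is an association with DC release, which a Pearson correlation does test, and the text also uses the language of exploration. This limits the point to the inference about site.

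The magnitude depends on an assumed ρ and on an r taken from another group and another rating; at r = 0.21 the effect is small. That stands, and the figures are an illustration only.

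Finally, any regional contrast is weak at 20–25 per group. That is a reason to say beforehand what can be concluded, not to leave the contrast out.

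**Conclusion.** The point holds in a limited form. As planned, a significant DC–anxiety correlation in REC AN shows that anxiety tracks release in a region that includes the site of interest. It cannot show that the link is specific to the DC rather than to the AVS or to the striatum as a whole.

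How often this ambiguity would arise depends on quantities the documents do not give. It is common if regional release is at least moderately correlated and the rating link is strong (DC significant in 18–90% of AVS-only trials over n = 20–25), and uncommon if the link is near 0.21 (7–14%). These are not error rates for the site conclusion. No sample size, primary comparison or decision about a participant depends on it. This is a cheap improvement.

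**What to change.** In the Aim 2C analysis text:
1. Add, within REC AN, a Williams or Steiger comparison of the DC–anxiety and AVS–anxiety correlations as the test of regional specificity, and the matching AVS-against-DC comparison for euphoria in CW.
2. State that a DC-specific claim requires the DC correlation to exceed the AVS one. Otherwise report that anxiety tracks striatal release, with regional specificity exploratory.
3. Keep the region-by-region correlations as description, always showing both regions together.
4. A regression on both regions may be reported in support but is no substitute: when both contribute equally, its DC term is significantly positive in 10–83% of trials, against about 2.5% for Williams' test.

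The cost is some wording and one calculation on values already computed. The downside to state is low power: about 9–57% at 20–25 per group when the DC is the true site and r = 0.5–0.69, so a non-significant comparison does not refute DC specificity. Unequal measurement error in the two regions can also bias the comparison, and this should be noted as a limitation.

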**Table 2: Interviews and self-assessments**

Name	Abbreviation	Area assessed	Minutes
Interviews:			
Mini-International Neuropsychiatric Interview	M.I.N.I. Plus	Axis I diagnoses	60
Module H of SCID I, Modified	Module H	ED diagnoses	30
Yale-Brown Obsessive Compulsive Scale	Y-BOCS	OCD	30
Yale-Brown-Cornell Eating Disorder Scale	YBC	ED symptoms	15
Set-shifting	SS	Inflexibility	5
Self-Assessments:			
Beck Depression Inventory	BDI	Depression	10
Spielberger State-Trait Anxiety Scale-Version Y	STAI-Y	State and trait anxiety	10
Eating Disorders Inventory -2	EDI-2	Core ED symptoms	15
Multi-dimensional Perfectionism Scale	MPS	Perfectionism	10
Barrett Impulsivity Scale	BIS	Impulse control	10
Temperament and Character Inventory	TCI	Personality and temperament	30
Sensation Seeking Scale	SSS	Sensation Seeking	15

**Study-Day Session Procedures:** Each study will be done during the early follicular phase (days 1 to 10) of the subject's menstrual cycle. Subjects will arrive the day before the study and stay overnight at the Clinical and Translational Research Institute (CTRI) at UCSD. On the day of the study, they will be awakened at 6:00 A.M. by the research staff. After a light breakfast, they will be transported by taxi to the Keck Center for Functional Magnetic Resonance Imaging on the UCSD campus at 7:00 A.M. After the acquisition of the structural MRI, which will be completed in about 30 minutes, the subjects will be transported again by taxi to the UCSD NeuroPET Center. The subjects will be informed of all of the procedures that will be performed and the information that will be obtained. The subject confirmation will be made via the signed copy of the written informed consent and then an intravenous catheter will be placed in either the left or right antecubital vein. After insertion of an intravenous catheter in a forearm vein, and a 20 minute transmission scan, a PET scan will be acquired following a slow bolus administration (over 20 sec) of 15 mCi of high-specific activity [C]DASB. Emission data will be collected in 3D mode for 100 minutes using a standard PET protocol as previously

described. At the completion of the scan, the IV lines will be removed. An EKG, vital signs, mental status and physical exam will be performed and evaluated by the study physician prior to the subject's discharge from the PET suite.

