## 11. RECRUITMENT

This is a five-year study in which we will recruit equal numbers of subjects each year. It is our experience from previous studies that it will be necessary to enroll an additional 20% of subjects due to drug failure, non-completion of PET studies, etc. Thus, we expect to enter 30 subjects to complete cells of 25 radioligand/PET studies per subject group. Overall, we will enter 120 subjects into this study in 5 years or 24 subjects per year.

Since at least 50 to 70% of individuals who have anorexia or bulimia eventually recover, we are confident that our recruitment goal can be achieved over the proposed 5-year period. All CW will be recruited from the greater San Diego region to minimize travel cost. However, based on our experience, approximately 75% of our REC subjects will come from outside southern California.

We will continue to employ recruitment strategies that were effective in our previous studies. These include: a) mailings to former patients of UCSD and the University of Pittsburgh ED treatment programs and other nationally recognized ED treatment programs directed by colleagues; b) mailings of IRB approved flyers to clinicians and treatment centers specialized in EDs, and to university health and counseling centers; c) placing advertisements and study announcements in ED related publications, press releases and conferences (e.g., NEDA, AED and EDRS); d) placing study advertisements on websites such as EDReferral and NEDA. We will also utilize the UCSD research websites which make available to professionals and the lay public alike our research publications and current findings; e) We may also contact participants who have been in our previous studies and who appear to be appropriate potential participants for this current study, provided they have given written permission to recontact them. There will be no cold-calling to any potential participant.

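### Splitting REC AN into high and low state anxiety groups weakens the exploratory anxiety–SSRT sub-analysis and cannot show a curved relation; analyse the score as continuous

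*Combined protocol and SAP*

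**What the plan says.** The split appears in Section 7 (Background and Significance), in the inhibition part of the text on endogenous dopamine release: "We will stratify our AN population into high and low state anxiety groups". Its purpose is "to better understand the relationship between anxiety and response inhibition ability in this group", and then to see how this bears on the AMPH challenge and on a putative marker of endogenous dopamine. No cut-point, anxiety instrument, time point or test is given.

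Anxiety is recorded as a score in three places. Table 2 in Section 9 lists the "Spielberger State-Trait Anxiety Scale-Version Y" (STAI-Y), and the text before that table says the self-ratings are sent to participants' homes before the interview is scheduled. On the raclopride scan day, a visual analogue scale (VAS) with an anxious item and the POMS-B, which has a tension-anxiety factor, are completed before the baseline scan, before AMPH and then every 30 minutes. The stop signal task is run after the first raclopride scan and again shortly after the second.

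The Aim 2C paragraph of the Power and Statistical Analysis Plan does not mention the split. It uses Pearson correlations, relates dopamine release to anxiety ratings and, separately, to SSRT, and treats the inhibition measures as continuous. It has no analysis of state anxiety against SSRT.

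On sample size, Section 11 says "Thus, we expect to enter 30 subjects to complete cells of 25 radioligand/PET studies per subject group", while the Aim 2C power statement assumes 20 per group.

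**The concern.** The question is one of association within a single group: as state anxiety varies among REC AN women, how do stopping speed, its response to AMPH and dopamine vary with it? Reducing a graded score to two categories treats all women on one side of the cut as alike. That costs power in a group of 20 to 25, and it makes the answer depend on a cut-point that the plan does not state.

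There is a second difficulty. The Background motivates the split with the idea that low threat speeds stopping and high threat slows it. If anxiety acts that way, the relation may bend, and a comparison of two means cannot reveal a bend.

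At stake is the plan's own alternative explanation for slower stopping in AN, namely that anxiety rather than reduced dopamine activation contributes to it. A weak test of that explanation would leave it neither supported nor set aside.

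**Working it through.** **Inputs.** REC AN completers: 25 (Sections 10 and 11); Aim 2C power: 20 per group. Test level: 0.05, two-sided (Aim 2C). Cut-point, score distribution and size of the anxiety–SSRT correlation: not in the documents. They are assumptions here and are varied below.

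**Nearest stated figure.** No power is given for the high/low analysis. The Aim 2C figure concerns a difference between groups in correlations: "we will have power 0.91 to see a group difference at the 0.05 level (two-sided), with 20 subjects per group". With a Fisher z difference of 1.06 and a unit standard deviation on the z scale, a two-sample t-test with 20 per group gives 0.904, and the normal approximation gives Φ(1.06/√(2/20) − 1.96) = 0.918. The stated 0.91 is therefore reproduced on that basis. It does not involve the split, and nothing below depends on it.

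**Information kept by a cut.** If a normal score is cut so that a fraction q lies below, the squared correlation between the score and the high/low indicator is φ(z_q)² / [q(1 − q)]. This is the share of information kept for a linear relation.

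- Median cut: (1/2π)/0.25 = 2/π = 0.637, a loss of 36%. Then 25 women carry the information of 25 × 0.637 = 15.9, and 20 carry that of 12.7.
- 60/40 cut: 0.622 kept, a loss of 38%.
- 67/33 cut: 0.595 kept, a loss of about 40%.
- 75/25 cut: 0.318²/0.1875 = 0.539 kept, a loss of 46%.
- 80/20 cut: 0.490 kept, a loss of 51%.

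For a median cut of other score shapes, the losses are 25% (uniform), 41% (gamma with shape 4), 46% (t with 5 df) and 52% (exponential).

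**Power.** Simulation with 40,000 replicates, bivariate normal data, and a test of the correlation of SSRT with either the score or the indicator:

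| n | True r | Continuous | Median split | 75/25 split |
|---|---|---|---|---|
| 25 | 0.4 | 0.53 | 0.35 | 0.29 |
| 25 | 0.5 | 0.75 | 0.53 | 0.43 |
| 25 | 0.6 | 0.91 | 0.71 | 0.61 |
| 20 | 0.5 | 0.64 | 0.43 | 0.35 |

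As a cross-check, a median split shrinks a correlation of 0.5 to 0.5 × √0.637 = 0.40. The continuous test at r = 0.4 has power 0.525, and the split test at r = 0.5 has 0.526. The two agree.

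**Curvature.** If SSRT followed a symmetric U about the cut, the high and low groups would have equal mean SSRT and the split would show nothing. A straight line through the continuous score would also miss it; a quadratic term would not. With 25 women, a linear-plus-quadratic model leaves 25 − 3 = 22 residual degrees of freedom, against 23 for either the straight line or the two-group comparison.

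**The case against.** The strongest reply concerns scope. The split is one sentence in the Background, about one sub-question in one group. The Aim 2C analysis plan does not use it: dopamine release is correlated with anxiety and with SSRT as continuous quantities, and the predicted relation of SSRT to dorsal caudate binding is also unsplit. No sample size or power figure relies on it. All of this stands. A reader might infer that the response-inhibition analysis as a whole is compromised; the documents do not support that.

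A second reply is that the size of the loss is assumed. A reader might take a loss of one third, or 12 to 13 women per stratum, as facts of the plan. They are not: both need a median cut, and the 36% also needs a normal score and a linear relation. This stands too, and is why a range is given.

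Third, the split may be deliberate. If the true relation were a step at the cut, the two-group comparison would be the more efficient choice, and a straight-line covariate could miss the pattern the authors have in mind. This is a fair criticism of a purely linear alternative. It does not rescue the split, because no threshold is named and a two-group comparison cannot distinguish a step from a slope or detect a symmetric bend.

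Finally, the STAI-Y in Table 2 is not tied to the task sessions, so simply using it as a continuous score would not be enough. That is correct, and the fix uses scan-day ratings instead.

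**Conclusion.** The point holds for the exploratory sub-analysis of state anxiety and response inhibition within REC AN, and no further. There, the plan states an inefficient method and offers no continuous alternative.

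The loss is about 36% of the information under a median cut, a roughly normal score and a linear relation, and about 25% to 50% over the other cuts and shapes considered. In power terms this is a drop of about 0.2 at n = 25 for correlations of 0.5 to 0.6. For a normal score the median is the most favourable cut, so an uneven one would do worse; a flat score would lose less. Apart from power, a high/low contrast cannot test the bend that the Background's rationale implies.

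This is a worthwhile, low-cost improvement. It is not a threat to the main aims.

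**What to change.** In the Aim 2C paragraph of the Power and Statistical Analysis Plan, add a short statement for REC AN:

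- Analyse state anxiety as a continuous score against SSRT and against the change in SSRT after AMPH.
- Use a rating already collected on the scan day near each stop signal task, either the VAS anxious item or the POMS-B tension-anxiety factor. Name one of them and the time points in advance. The pilot data cited in the Background report that AMPH raised anxiety in REC AN, so a pre-AMPH and a post-AMPH rating could rank the women differently.
- Include a quadratic term to check for non-linearity.
- Label interactions with AMPH condition and with dorsal caudate binding as exploratory; the power figures above are for a single correlation and do not carry over to interactions in 20 to 25 women.
- Use "high and low state anxiety groups" for display only, and amend the Background sentence to match.

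No new data, visits or participants are needed. The cost is a few lines of text, the choice of instrument and time point, and one or two extra model terms in a small sample.
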